The reasons why a subject may discontinue or be withdrawn from the study by the investigator include, but are not limited to the following: subject request, protocol violation, loss to follow up, subject non-compliance, defined as 4 missed applications during the 2 week period between study Visits, study termination by investigators, and a confirmed grade 3 or higher adverse event, which is suspected to be related to study drug administration. Subjects that elect to withdraw from the trial due to lack of efficacy and/or exacerbation of disease will undergo the following: vital signs; blood test; pregnancy test (if applicable); clinical photography; SD clinical assessments; DLQI questionnaire, assessment of concomitant medication and adverse events; blood collection for future mechanistic analysis; lesional tape strip collection.

Stopping Rules

Patients will be permanently discontinued from study treatment in the event of:

- Anaphylactic reaction or other severe systemic reaction to study drug application
- Pregnancy at anytime during the study period
- Diagnosis of a malignancy during study, excluding carcinoma in situ of the cervix, or squamous or basal cell carcinoma of the skin
- Any infection that is opportunistic, whose nature or course may suggest an immuno-compromised status
- Treatment with any prohibited concomitant medication or procedure
- Other reasons that may lead to the permanent discontinuation of study drug include certain Aes deemed related to the study drug.
- If the following lab results are abnormal, participants will be retested in a window of 7-10 days and reassessed. If the test results remain abnormal, participants will be discontinued from the study:

Hematology

Absolute Neutrophil Count: $<1000/\text{mm}^3$; $<1.0 \times 10^9/\text{L}$

Hemoglobin: $<8.0 \text{ g/dL}$; $<4.96 \text{ mmol/L}$; $<80 \text{ g/L}$

Hemoglobin drop $\geq 2 \text{ g/dL}$ from baseline on two consecutive blood draws with associated symptoms; or hemoglobin drop $\geq 3 \text{ g/dL}$ from baseline on two consecutive blood draws without associated symptoms.

Platelet count: $<75,000/\text{mm}^3$; $<75.0 \times 10^9/\text{L}$

Lymphocytes: $<500/\text{mm}^3$; $<0.5 \times 10^9/\text{L}$

Chemistry

AST $>3.0 \times \text{ULN}$

ALT $>3.0 \times \text{ULN}$

Total bilirubin $>1.5 \times \text{ULN}$

CPK $>10 \times \text{ULN}$

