An "Initial Pregnancy Report" or equivalent must be completed in full and emailed to [contact] or faxed to [name] within 24 hours of discovery of a pregnancy of a subject who has taken the Incyte product or the pregnancy of a partner for a subject who has taken the Incyte product. The "Follow-up Pregnancy Report Form" or equivalent must be completed and emailed to [contact] or faxed to [name] within 30 days after delivery, so that Incyte is provided with information regarding the outcome of the pregnancy. If the pregnancy results in any events which meet the serious criteria (i.e., miscarriage or termination), the SAE reporting process needs to be followed and the timelines associated with a SAE should be followed.

SUBJECT IDENTIFICATION

Subjects are numbered sequentially. Each subject will be assigned a unique screening number for the duration of the study. Subject screening numbers will not be reassigned or reused for any reason. The investigator must maintain a master log linking the subject number to the subject's name. The investigator must follow all applicable privacy laws in order to protect a subject's privacy and confidentiality.

STUDY DRUG SUPPLY:

Seborrheic Dermatitis Ruxolitinib Cream Protocol
Incyte IIR
March 25, 2022

Eligible patients will receive a supply of ruxolitinib 1.5% cream which they will apply to affected skin on the face only twice daily. Patients will be instructed not to use more than 60g of cream per week.

All study medication will be stored in a secure cool area between 15-30°C. Study drug will be provided to subjects at each study visit, with initial application performed at that time and subsequent applications performed by the patients at home.

Subjects will be queried during each study visit on any missed applications.

STATISTICAL CONSIDERATIONS:

Sample Size Calculation

A sample size of n=20 SD patients guarantees 90% power at 2.1% significance to detect a minimum proportion of 75% of patients with IGA 0/1 at week 4. This calculation assumes the application of the one-sided binomial test with a null hypothesis proportion of 40%. This proportion is based on the vehicle response benchmark reported by Zirwas et al.(2021) when comparing IGA 0/1 at week 8 in 154 patients treated with roflumilast foam 0.3% vs. 72 patients in the vehicle-controlled group(18). Accounting for a 20% dropout rate, we, therefore, propose a sample size of n=25 patients.

Mechanistic Endpoint

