To the best of our knowledge, this is the first study to evaluate differences in the transcriptome between SD and healthy subjects. A previous study (19) evaluated a fold-change (FCH) of 5 in IL-10 cell counts with coefficient of variation of 50% when comparing 10 SD subjects to 4 healthy volunteers. Assuming similar variability, a sample size of n = 20 SD subjects and n= 20 controls would provide 90% power at 5% significance to detect FCH>2.65 when comparing IL-10 expression between SD and controls, based on a two-sided unpaired t-test applied to log2-transformed RNA-seq data and fold-changes back transformed.

Demographics and Other Baseline Characteristics

Descriptive statistics of demographics and other baseline characteristics of patients will be summarized. Other baseline characteristics include height, weight, vital signs, duration of SD disease, concurrent diagnoses from medical history and indications for concomitant medication, concomitant medication, and previous SD treatments.

Analysis of Primary Endpoint

The one-sided binomial test will be used to verify the hypothesis that the proportion of patients achieving IGA 0/1 at 4 weeks of treatment with ruxolitinib 1.5% cream applied twice daily is greater than 0.4.

Analysis of Secondary Endpoints

The two-sided Wilcoxon signed-rank test will assess the significance of changes from baseline in:

- IGA score at 4 weeks of treatment
- Components of clinical SD scoring (scale, erythema, and pruritus) at 4 weeks of treatment.

The two-sided paired t-test will assess the significance of changes from baseline in:

- Overall clinical SD scoring at 4 and 6 weeks of treatment.
- Vital signs measured in interval or ratio scale
- Analytes measured in interval or ratio scale from laboratory tests (hematology, serum, chemistry, and urinalysis) at 4 weeks of treatment

The p-values will be adjusted by the Bonferroni method. The frequency, duration, and severity of AEs will be summarized with tables and summary statistics.

Analysis of Mechanistic (Exploratory) Endpoints

The baseline immune and molecular cutaneous profile of SD at baseline compared with healthy controls and the change in the immune and molecular cutaneous profile of SD with treatment will be assessed by MMRM approach. Gene/Protein expression data will be modeled using a mixed effect model with the interaction between tissue type (non-lesional/ lesional / healthy) and timepoint as fixed effects and a random effect for each subject.

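### The paired t-test for the overall SD Severity Score has no missing-score rule and makes no use of the Week 2 or Early Termination scores, so it overstates improvement if poor responders leave more often.

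*Combined protocol and SAP*

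**What the plan says.** All references are to the combined protocol and SAP.

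- **Overall score.** Under Analysis of Secondary Endpoints, "The two-sided paired t-test will assess the significance of changes from baseline in" several measures, the first being "Overall clinical SD scoring at 4 and 6 weeks of treatment".
- **Ordinal scores.** In the same section, "The two-sided Wilcoxon signed-rank test will assess the significance of changes from baseline in" the IGA at Week 4 and "Components of clinical SD scoring (scale, erythema, and pruritus) at 4 weeks of treatment".
- **Dropout.** Sample Size Calculation: "Accounting for a 20% dropout rate, we, therefore, propose a sample size of n=25 patients".
- **Reasons for leaving.** The section on discontinuation and withdrawal lists subject request, protocol violation, loss to follow-up, non-compliance and related adverse events of grade 3 or higher. It then adds: "Subjects that elect to withdraw from the trial due to lack of efficacy and/or exacerbation of disease will undergo the following", followed by exit procedures that include the SD clinical assessments.
- **Scores collected.** The visit procedures and Table 1 schedule the IGA and SD Severity Score at Screening, at Weeks 0, 2, 4 and 6, and at Early Termination.

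Statistical Considerations defines no efficacy analysis set, no rule for a missing score and no sensitivity analysis. It names no efficacy test that uses Week 2, and it does not say whether an Early Termination score may stand in for Week 4 or Week 6.

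**The concern.** A paired test needs both values. With no imputation or substitution rule, the natural reading is that a patient without a Week 4 or Week 6 score is left out of that test. The mean change then describes those who stayed. It estimates the change in all treated patients without bias only if leaving is unrelated to response.

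The protocol itself names a route by which poor responders leave. The trial is open-label with no vehicle arm, so mean change from baseline is itself the efficacy estimate, and no comparator suffers the same selective loss to offset it. Meanwhile the Week 2 and Early Termination scores, which carry information on how dropouts were doing, are collected and given no role in the efficacy analysis.

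**Working it through.** **1. The plan's own figures.** Sample Size Calculation says "A sample size of n=20 SD patients guarantees 90% power at 2.1% significance to detect a minimum proportion of 75% of patients", against a null proportion of 40%. With 20 patients and success at 13 or more responders, the exact binomial gives alpha 0.0210 and power 0.898, and 20 / (1 - 0.20) = 25. Both reproduce. They concern the primary endpoint only. No effect size, SD or power is stated for the secondary tests.

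**2. Bias by arithmetic.** Let d be the dropout fraction, C the mean improvement in completers and D the mean improvement that dropouts would have had.

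- Mean in all treated patients = (1 - d) x C + d x D
- Overstatement by complete pairs = C - [(1 - d) x C + d x D] = d x (C - D)

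Take d = 0.20 from the plan and assume C = 4 points on the 0-12 scale:

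| D | Overstatement |
|---|---|
| 0 | 0.20 x 4 = 0.8 |
| 2 | 0.20 x 2 = 0.4 |
| 4 | 0 |
| 5 | 0.20 x (-1) = -0.2 (understated) |

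**3. Bias by simulation, Week 4.** The documents give no mean or SD of change and no dropout mechanism, so these inputs are assumptions: 25 patients, true mean change -4.0, SD 2.5, Week 2 to Week 4 correlation 0.5 to 0.85, five patients leaving after Week 2, 20,000 trials per case. The complete-pair mean is compared with a likelihood estimate that also uses Week 2. A negative bias means improvement is overstated.

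| Who leaves | Bias, complete pairs | Bias, using Week 2 |
|---|---|---|
| Unrelated to response | 0 | 0 |
| More often after a poor Week 2 result (slope 1 per SD) | about -0.2 to -0.4 | about 0 |
| The five worst at Week 2 | about -0.4 to -0.7 | about 0 |
| More often with a poor, unseen Week 4 score (slope 1.5 per SD) | about -0.6 | -0.48 (correlation 0.5) to -0.21 (correlation 0.85) |
| More often after a good Week 2 result (slope 1 per SD) | about +0.2 to +0.4 | about 0 |

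Hand check of the third row: in a large sample, removing the worst 20% shifts the Week 2 mean by 0.280 / 0.80 = 0.35 SD. The Week 4 shift is 0.35 x 2.5 x correlation, that is 0.44 at 0.5 and 0.74 at 0.85, close to the simulated values for 25 patients.

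**4. Precision.** With dropout unrelated to response, the standard error using Week 2 is 2% to 8% smaller than that of the complete-pair mean. If the five worst leave, it can be up to about 8% larger.

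**5. Effect on the test.** With 20 pairs, SE = 2.5 / sqrt(20) = 0.56 and t = 4.0 / 0.56 = 7.2. Taking the largest Week 2-related bias off the true change gives 4.0 - 0.71 = 3.29 and t = 5.9, p about 1e-5.

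**The case against.** A reader might infer that the estimate is biased towards responders, or that it will overstate improvement. The documents do not support that. The 20% is a sample-size allowance with no mechanism attached. Withdrawal for lack of efficacy is provided for, but so are several reasons that need not depend on response, and the bias vanishes or reverses under some of the patterns above.

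Nor does the plan say that only complete pairs are used. That is the default when no rule is given. Early Termination scores are not excluded; their use is unspecified.

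Three further objections stand in part:

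- **Limits of the model.** Using Week 2 removes bias fully only when dropout depends on observed scores. If it depends on the unseen Week 4 score, about 20% to 67% of the bias is removed, depending on the correlation. Patients who leave before Week 2 have no Week 2 visit score to use.
- **Significance.** Under the assumed values the test result would not change, even after the "The p-values will be adjusted by the Bonferroni method" step for any plausible number of tests. What is at stake is the size of the estimate.
- **Choice of method.** Paired and signed-rank tests are standard in a 25-patient single-arm study, and a rank test suits five-level items. This is a good reason to keep Wilcoxon for the IGA and components. It is not a reason to leave the overall score without a missing-score rule.

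**Conclusion.** The concern holds in conditional form. The plan leaves the handling of missing overall SD scores unstated and gives no role to collected scores that bear on it. If poor responders leave more often, mean improvement is overstated by 0.20 times the completer-dropout difference. At Week 4, under the assumed values, that is about 0.2 to 0.4 points (0.2 / 4.0 = 5% to 0.4 / 4.0 = 10%), and up to about 0.7 points (0.7 / 4.0 = 18%) in the extreme case.

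These sizes rest on an assumed mean, SD, correlation and dropout pattern. The same direction of risk applies at Week 6, but that visit falls two weeks after treatment ends and no size was computed for it. The primary endpoint's test is not touched by this point. The change is worth making because the data are already collected and, when nobody drops out, the model gives essentially the same mean change as the paired analysis.

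**What to change.** 1. Analyse change in the overall SD Severity Score with a repeated-measures model: Weeks 2, 4 and 6 as a factor, baseline score as covariate, unstructured covariance.
2. Define the analysis set as every treated patient with a baseline score and at least one later score.
3. Assign an Early Termination score to the next scheduled visit not yet attended, so that it never displaces an existing score.
4. Report mean change with 95% CI at Weeks 4 and 6, and keep the paired t-test as a supporting analysis.
5. Add a sensitivity analysis that sets dropouts to no change from baseline, because the model does not fully remove bias when dropout depends on unseen scores.
6. Keep the Wilcoxon signed-rank test for the IGA and the 0-4 component scores.

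The cost is plan wording and standard code, with no new data or visits. The plan already specifies a repeated-measures approach for the molecular data, so the method is within the team's reach. The downsides are a few more model parameters with 25 patients, and a standard error up to about 8% larger if only the worst responders leave.

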- Change from baseline in overall clinical SD score at 4 weeks of treatment with ruxolitinib 1.5% cream applied twice daily

- Change from baseline in each component of the clinical SD score at 4 weeks of treatment with ruxolitinib 1.5% cream applied twice daily (scale, erythema, pruritus)
- Change in overall clinical SD at 6 weeks (i.e., 2 weeks after treatment cessation) from baseline and from 4 weeks
- The frequency, duration, and severity of AEs
- Changes in vital signs
- Changes in laboratory data for hematology, serum chemistry, and urinalysis

Mechanistic (Exploratory) Endpoints

- Determine the molecular cutaneous phenotype of SD at baseline compared with healthy controls, using transcriptomic and proteomic approaches from skin samples acquired by tape-strips
- Identify molecular markers that correlate with disease activity in SD at baseline
- Characterize the change in molecular responses with treatment of topical ruxolitinib 1.5% cream after 4 weeks of treatment
- Identify molecular markers that correlate with treatment response at 4 weeks

STUDY DESIGN OVERVIEW:

This study is an open-label prospective interventional trial. The study will take place at Icahn School of Medicine at Mount Sinai.

The study will include 25 adult patients with moderate-to-severe-SD as well as 20 age- and gender-matched healthy control subjects for comparison. The SD patients will have baseline clinical score of at least 6 using the SD Severity Score in Appendix 1, or an Investigator Global Assessment (IGA) score of at least 3. Enrolled SD subjects will apply topical ruxolitinib 1.5% cream twice daily for 4 weeks. They will return for visits at weeks 2, 4, and 6 following study treatment initiation for repeat clinical assessments, medication reviews, tape-strip, blood and urine sample collections, and monitoring for adverse events.

After providing consent, all subjects will be assessed for study eligibility, which includes a review of the subjects past and current medical conditions, familial medical history and detailed review of past and current medications. SD subjects will also undergo a review of past topical treatments/therapies for SD, and clinical assessments (clinical SD score and IGA).

Subjects who meet inclusion criteria for eligibility may continue with the Baseline Visit (Week 0) or can be scheduled to return for the Baseline Visit within 28 days of the Screening Visit.

SD Subjects:

Seborrheic Dermatitis Ruxolitinib Cream Protocol
Incyte IIR

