March 25, 2022

At Baseline/Week 0, subjects will undergo clinical assessments (clinical SD Severity Score and IGA), review of concomitant medications, standardized clinical photography, and a Dermatology Life Quality index (DLQI) questionnaire (Appendix 2). Subsequent clinical assessments including standardized clinical photography, and questionnaire completion will be performed at follow up visits at Week 2, Week 4, and Week 6. Skin tape-strip samples will be collected for mechanistic studies (described below) at baseline (lesional and non-lesional facial skin), Week 2 (lesional facial skin), Week 4 (lesional facial skin), and Week 6 (lesional facial skin). Additional blood samples will be collected and stored at baseline and at Week 4 (or early termination, whichever is first) for potential future mechanistic analyses.

Control Subjects:

At Baseline/Week 0, subjects will undergo a review of concomitant medications, skin tape-strip samples will be collected for mechanistic studies (described below) of non-lesional facial skin, blood and urine sample collection for standard laboratory testing, and a blood sample for possible future mechanistic analyses.

MECHANISTIC ANALYSES:

We will characterize the molecular immune profiles of patients with SD at week 0 and week 4, with comparison to baseline profiles in healthy control subjects.

We plan to obtain lesional and non-lesional tape strip samples from facial skin of SD patients at week 0 and lesional facial skin samples at Week 4 (Primary Endpoint). Additionally, lesional facial skin samples will be collected at Week 2 and Week 6 and stored for potential future analysis. Blood samples at baseline and at Week 4 will be collected and stored for potential future analysis.

Gene expression studies on tape strip samples will be performed using Illumina NovaSeq 6000 for RNA-seq, and proteomic studies on tape strip samples will be performed using the Olink Explore panel, which includes >1,500 protein analytes.

PATIENT POPULATION:

Prior to enrollment, all subjects must meet the following inclusion and exclusion criteria:

Inclusion Criteria For SD Subjects:

- 1) Male or female subjects \geq 18 years of age at the time of signing the informed consent document.
- 2) Subject is able to understand and voluntarily sign an informed consent document prior to participation in any study assessments or procedures.

- 3) Subject is able to adhere to the study visit schedule and other protocol requirements.

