- SD clinical assessments (IGA, SD Severity Score)
- Urine pregnancy test for all female subjects of child-bearing potential
- Collect blood samples for CBC with differential, Comprehensive metabolic panel (CMP), and C-reactive protein (CRP)
- Collect blood sample for possible future mechanistic analyses
- Urinalysis
- Perform tape strips of lesional skin. Lesional skin tape strips will be taken from the same location as the lesional tape strips taken at Baseline and Week 2.
- Assess study drug dosing compliance and retrieve all remaining study drug from subject. Subjects will report each study drug application, with 4 missed doses from Week 2 considered non-compliance.

Visit 5 – Week 6

- Record concomitant medications and adverse events
- DLQI questionnaire

- Standardized clinical photography including photographs of subject's entire face and close up photographs of the following facial regions: 1. Left cheek, 2. Right cheek, 3. Forehead and glabella)
- SD clinical assessments (IGA, SD Severity Score)
- Urine pregnancy test for all female subjects of child-bearing potential
- Perform tape strips of lesional skin. Lesional skin tape strips will be taken from the same location as the lesional tape strips taken at Baseline, Week 2, and Week 4.

Early Termination Visit (if applicable)

- Record concomitant medications and adverse events
- DLQI questionnaire
- Standardized clinical photography (including photographs of subject's entire face and close up photographs of the following facial regions: 1. Left cheek, 2. Right cheek, 3. Forehead and glabella)
- Urine pregnancy test for all female subjects of child-bearing potential
- Collect blood samples for CBC with differential, Comprehensive metabolic panel (CMP), and C-reactive protein (CRP)
- Collect blood sample for possible future mechanistic analyses
- Urinalysis
- SD clinical assessments (IGA, SD Severity Score)
- Perform tape strips of lesional skin. Lesional skin tape strips will be taken from the same location as the lesional tape strips taken at Baseline and Week 2 (if applicable)
- Assess study drug dosing compliance and retrieve all remaining study drug from subject

For Control Subjects

Visit 1 – Screening (within 28 days of Baseline)*

- Obtain signed IRB-approved informed consent and HIPPA agreement
- Review Inclusion and Exclusion Criteria
- Record gender, race, ethnicity, and medical history
- Review personal and family medical conditions/diseases

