Safety will be evaluated by tabulations of adverse events (AEs) and will be presented with descriptive statistics at each visit. AEs will be coded using the CTCAE, Common Terminology Criteria for Adverse Events, V 5.0. The number and percentage of subjects/lesions experiencing an AE/SAE will be stratified by system organ class, or a preferred term, and/or severity of the adverse event, and recorded and tabulated overall by each sub-strata. Each subject will be counted only once within a system organ class or a preferred term using the adverse events with the highest severity within each category. All information pertaining to adverse events noted during the study will be listed by subject, detailing verbatim given by the investigator, preferred term, system organ class, date of onset, date of resolution, severity, and relationship to treatment. A tabulation of AEs will be provided by subject.

DLQI (Dermatology Life Quality Index)

The DLQI is a validated questionnaire consisting of 10 questions that has been used in many randomized controlled trials in dermatology (20, 21).

Scoring

The scoring of each question is as follows:

Very much	scored 3
A lot	scored 2
A little	scored 1
Not at all	scored 0
Not relevant	scored 0

Question unanswered	scored 0
---------------------	----------

The DLQI is calculated by summing the score of each question. The maximum score is 30 and minimum score is 0. Higher score represents a quality of life that is more impaired.

Definition of DLQI Scores

0-1 = no effect at all on patient's life

2-5 = small effect on patient's life

6-10 = moderate effect on patient's life

11-20 = very large effect on patient's life

21-30 = extremely large effect on patient's life

A change in DLQI score of at least 4 points is considered clinically important (22). Such change suggests that there has actually been a meaningful change in that patient's quality of life since the previous measurement of his/her DLQI scores.

Table 1. Schedule of Events

Visit Week	(Up to -28 Days before Baseline)	0	2	4	6	X	Control Subjects
Visit #	1	2	3	4	5	Early Termination	1
Visit Type	Screening	Baseline	Tx	Tx	F-up		Screening / Baseline
Informed Consent	X						X
Inclusion / Exclusion Criteria	X	X ³					X
Demographics and Medical Hx¹	X						X
Urine Pregnancy Test	X	X ³	X	X	X	X	X
CBC w/differential; CMP; Urinalysis		X		X		X	X
Blood Sample Stored for Future Analysis		X		X		X	X
CRP		X		X			X
SD Clinical Assessments (IGA, SD Severity Score)	X	X ³	X	X	X	X	

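### Laboratory change is tested only at Week 4, so Early Termination labs from patients with no Week 4 draw enter no planned laboratory summary

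*Combined protocol and SAP*

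**What the plan says.** The Secondary Endpoints list includes "Changes in laboratory data for hematology, serum chemistry, and urinalysis" and gives no time point. Analysis of Secondary Endpoints supplies one. Under the lead-in "The two-sided paired t-test will assess the significance of changes from baseline in" it names "Analytes measured in interval or ratio scale from laboratory tests (hematology, serum, chemistry, and urinalysis) at 4 weeks of treatment", and then adds that "The p-values will be adjusted by the Bonferroni method".

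Table 1 has a row for "CBC w/differential; CMP; Urinalysis", marked for SD patients at Baseline, Week 4 and Early Termination. There is no mark at Week 2 or Week 6. The Early Termination visit list agrees on blood count, metabolic panel and urinalysis, and its blood item reads "Collect blood samples for CBC with differential, Comprehensive metabolic panel (CMP), and C-reactive protein (CRP"). The CRP row of Table 1, however, has no Early Termination mark.

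For stored research blood, the Study Design Overview does say what happens when a patient leaves early: "Additional blood samples will be collected and stored at baseline and at Week 4 (or early termination, whichever is first"). No similar rule is given for the analysis of the safety labs.

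Analysis of Safety and Tolerability describes adverse event tabulations and listings and does not mention laboratory values. Safety Evaluation names adverse events, physical examinations and vital signs. Safety Monitoring says that an investigator reviews all laboratory results and assesses them for adverse events.

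**The concern.** A paired test needs two values per patient. With no Week 2 draw, the Early Termination sample is the only scheduled post-baseline safety lab for someone who leaves before Week 4, and the plan gives it no place in the endpoint. The result is in effect a summary of patients who reached Week 4.

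Leaving early need not be unrelated to laboratory change. The reasons for withdrawal include "a confirmed grade 3 or higher adverse event, which is suspected to be related to study drug administration", and the stopping rules add systemic reactions and opportunistic infections. The trial has a safety objective and no concurrent control, so a mean change among those who reached Week 4 cannot by itself speak for all treated patients. The missing values would already have been collected.

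**Working it through.** **1. The plan's own figures.** The documents give no sample size or power for the laboratory endpoint. The dropout allowance comes from the primary sample size, so I checked that first.
- Inputs (Sample Size Calculation): n = 20, null proportion 0.40, alternative 0.75, one-sided exact binomial test, 20% dropout.
- Rule: success if at least 13 of 20 respond.
- P(X ≥ 13 | 20, 0.40) = 0.0210, against the stated 2.1%.
- P(X ≥ 13 | 20, 0.75) = 0.898, against the stated 90%.
- 20 / (1 − 0.20) = 25, as stated.

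The design reproduces.

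**2. What is drawn and what is analysed (SD patients).**

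| Draw | Blood count, metabolic panel, urinalysis | Place in a planned laboratory analysis |
|---|---|---|
| Baseline | yes | yes, first half of the pair |
| Week 2 | no | – |
| Week 4 | yes | yes, second half of the pair |
| Week 6 | no | – |
| Early Termination | yes | none stated |
| Retests under the stopping rules | as needed | none stated |

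The plan has no visit window, last-value rule, missing-data rule or safety population that would move an Early Termination value into the Week 4 slot.

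**3. How many patients.** The planned dropout is 0.20 × 25 = 5. If all five leave before Week 4, the test uses 20 of 25 patients. If all five leave after Week 4, it uses 25 of 25. The documents do not say which, so the range is 0/25 to 5/25, or 0% to 20%. The number whose data could be recovered may be smaller. Patients lost to follow-up have no Early Termination labs, and Study Withdrawal lets the final visit cover only part of its list.

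**4. What a Week 4-only mean can miss.** Let m patients have Early Termination labs only, with mean change d, and let the rest have mean change 0 at Week 4. The Week 4 mean is then 0 and the all-treated mean is m × d / 25. With m = 5 this is 0.2d, so d = −1, −2 or −3 units gives −0.2, −0.4 or −0.6. The values of d are assumptions, since the documents give none.

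**5. Whether a mean alone is enough.** Assume, purely for illustration, that three of five early leavers have an ALT rise of 60 U/L and the other 22 patients have no change.
- Week 4 only (20 patients): mean 0.
- With Early Termination labs (25 patients): mean = 3 × 60 / 25 = 7.2 U/L.
- Sum of squares = 3 × 60² − 25 × 7.2² = 10,800 − 1,296 = 9,504.
- SD = √(9,504 / 24) = √396 = 19.9, and the standard error is 19.9 / √25 = 3.98.
- t = 7.2 / 3.98 = 1.81 on 24 degrees of freedom, two-sided p = 0.083 before the Bonferroni adjustment.

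Even with the values included, the planned test would not be significant. A shift table or listing would show three affected patients directly, so moving the values into the mean is only part of the remedy.

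**The case against.** The strongest reply is that the safety signal is not lost. Nothing in the plan excludes Early Termination labs, an investigator reviews every result, and an abnormality judged to be an adverse event is tabulated and listed with no restriction to Week 4. This stands. A reader might infer that the labs of patients stopped for safety vanish from all safety reporting, and the documents do not support that. What has no route is the measured change itself, including any shift that is not judged to be an event.

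A reader might also infer that everyone who stops the cream is lost, or that the result is biased towards no change. Neither is established. A patient taken off treatment who still attends Week 4 is counted. Withdrawal also covers subject request, loss to follow-up, protocol violation and non-compliance. With no scheduled on-treatment safety lab before Week 4, early safety stops would mostly follow clinical events, which need not come with laboratory change.

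Two further points on the other side are fair. A fixed Week 4 comparison is a legitimate analysis with equal follow-up. And the rule for stored blood concerns possible future research, so its absence for safety labs is not a contradiction; it shows only that the convention was available.

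**Conclusion.** The point holds for the laboratory-change endpoint. As written, its only analysis uses patients with a Week 4 draw, and no other planned output shows Early Termination laboratory values. The size is 0 to 5 of 25 treated patients. This assumes the planned 20% dropout, and the upper end requires that all dropouts leave before Week 4. The number with usable Early Termination labs may be lower. The direction of any bias is plausible but unproven, and adverse event reporting remains a partial safeguard. The primary endpoint is not touched. The change is still worth making, because the stated rule yields a summary of those who reached Week 4 for a secondary safety endpoint when data on the others are already to be collected.

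Separately, the Early Termination visit text and Table 1 disagree on whether CRP is drawn there and must be reconciled. Blood count, metabolic panel and urinalysis are not affected.

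**What to change.** In Analysis of Secondary Endpoints, define laboratory change as baseline to the last on-treatment value (Week 4, or Early Termination if earlier), in all treated patients with a post-baseline sample. Keep the Week 4-only test as supportive, and say that it does not add to the Bonferroni family, whose size the plan does not state.

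In Analysis of Safety and Tolerability, add a shift table from baseline and a by-patient listing of all post-baseline labs, including Early Termination and unscheduled draws. State how many treated patients have no post-baseline sample.

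Reconcile the Early Termination visit list with Table 1 on CRP.

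The cost is a few sentences, one table and one listing, with no new procedures or patients. The downside is that time on drug at the last value will differ between patients, so report exposure time next to the result.
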